8.2.3. EU Setting Considerations

8.3. Variables

8.3.1. Definitions

[figure not shown]
The following definitions apply to the different timings of data collection (see [Figure 2](#)):

- **Index date** is defined as the time of the first (non-missing) dose of belantamab mafodotin.
- **The baseline period** for data collection is defined as the time from the initial MM diagnosis until the index date (the first dose of belantamab mafodotin).
- **The post-index period** spans from the index date until the end of follow-up at 15 months, study discontinuation for any reason, informed consent withdrawal or death; whichever comes first.
- **The post-index treatment period** is defined as the duration of the belantamab mafodotin line of treatment (DoT). This spans from the index date until the confirmed decision date of permanent discontinuation of belantamab mafodotin treatment, the

confirmed date of a new line of treatment or the date of the end of follow-up at 15 months, study discontinuation for any reason, informed consent withdrawal or death; whichever comes first.

- **The study period** spans from the time from the initial MM diagnosis until the end of follow-up at 15 months, study discontinuation for any reason, informed consent withdrawal or death; whichever comes first.
- **Active treatment exposure periods** are defined as the time that belantamab mafodotin is considered to have a treatment effect during the post-index treatment period. This period includes all doses occurring within 70 days of the previous dose (belantamab mafodotin's half-life) from the date of the first belantamab mafodotin dose of that sequence to the date of the last dose +70 days or the date of the end of the post-index treatment period; whichever comes first.

Figure 2 Timings of Data Collection

[figure not shown]
Abbreviations: MM=multiple myeloma.

The following definitions apply to collection of treatment data:

- **Line of treatment** is defined as one or more completed cycles of a single agent, a regimen consisting of a combination of several drugs, or a planned sequential therapy of various regimens (Rajkumar, 2015).
- **A treatment cycle** is defined as the belantamab mafodotin label-approved dosing interval, which is 21 days (with a real-world scheduling grace period of +7 days).
- **Treatment discontinuation** is defined as a recorded clinician decision (with an associated decision date) to permanently discontinue belantamab mafodotin treatment.
- **Treatment interruption** is defined as withholding ≥ 1 belantamab mafodotin dose for any reason without a confirmed clinician decision to permanently discontinue treatment or initiate a new line of treatment. The time interval between doses will be >2 treatment cycles (+ 7-day grace periods).
- **Treatment delay** is defined as a delay (intentionally or unintentionally) in receiving belantamab mafodotin without skipping a dose. The time interval between doses will be >1 treatment cycle (+ a 7-day grace period) and <2 treatment cycles.

Figure 3 shows examples of treatment sequences that patients might undergo during the 15-month follow-up period.

Figure 3 Examples of treatment sequences during the post-index period

The following definitions apply to derived outcomes for statistical analyses:

- ORR is defined as the proportion of patients with a best response (sCR, CR, VGPR or partial response [PR]) during the study period evaluated by a responsible physician based on International Myeloma Working Group [IMWG] criteria if feasible or to local standard practice
- OS is defined as the time in months from the start of belantamab mafodotin treatment to the date of death due to any cause
- rwPFS is defined as the time in months from the start of belantamab mafodotin treatment to the date of the first documented disease progression or death, whichever occurs first
- DoR is defined as the time from the first documented evidence of PR or better until the earliest date of progressive disease (PD) or death among patients who achieved a response

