8.7.2.4. Analysis of Other Secondary Objectives

In addition, the following will be described for the SP (overall and by line of treatment):

- Exposure-adjusted incidence rate with 95% CI, overall and by SOC and PT names
 - Defined as the number of patients with at least one (specific) AE during follow-up divided by the sum of person-months at risk in the study.
 - Person-months at risk is defined as the duration of follow-up for patients without AEs plus the duration of follow-up until the date of the first (specific) AE for patients with an AE.
- Exposure-adjusted event rate with 95% CI, overall and by SOC and PT names
 - Defined as the number of (specific) AESIs during follow-up divided by the sum of person-months at risk in the study.
 - Person-months at risk is defined as the duration of follow-up.
- For patients with dose reductions, interruptions/delays or discontinuation of belantamab mafodotin treatment **due to an ocular AESI** during the study period, the following will be summarized (overall and by comorbidity, ocular AESI type and ocular AESI severity as well as treatment dose and frequency):
 - Number and proportions of patients
 - Primary reasons for dose reductions, interruptions/delays or discontinuation of treatment due to any AE
 - Belantamab mafodotin treatment patterns after occurrence of an ocular AESI (i.e., order of treatment changes and timing)

- Median, 95% CIs and 25th and 75th percentiles using the Kaplan-Meier (KM) method for time to dose reductions, interruptions/delays or discontinuation
- Duration of dose reductions and interruptions/delays or discontinuations
- Belantamab mafodotin treatment adherence, i.e., the total duration of treatment in days divided by the total follow-up time in days.
- Belantamab mafodotin treatment persistence, i.e., the proportion of patients still on treatment at specified time points, including 3-, 6-, 12- and 15-months of follow-up
- Treatment response (e.g., sCR, CR, VGPR or PR):
 - Best treatment response during follow-up
 - Treatment response at specified time points, including 12- and 15-months of follow-up
 - Proportion of patients with a maintained response (PR or better) at specific time points, including 12- and 15-months of follow-up
 - ORR with 95% CIs calculated based on the exact binomial distribution (Clopper-Pearson method)
- Median, 95% CIs and 25th and 75th percentiles using the KM method for:
 - OS (overall and based on response / non-response to treatment)

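### Duration of treatment never looks at the last dose, so a dose held and never resumed counts as treatment until some other end event

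*Protocol*

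**What the plan says.** Protocol Section 8.3.1 makes the post-index treatment period and DoT the same thing. The definition reads "This spans from the index date until the confirmed decision date of permanent discontinuation of belantamab mafodotin treatment, the" and continues "confirmed date of a new line of treatment or the date of the end of follow-up at 15 months, study discontinuation for any reason", then consent withdrawal or death, whichever comes first.

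Stopping has one definition. Treatment discontinuation "is defined as a recorded clinician decision (with an associated decision date) to permanently discontinue belantamab mafodotin treatment". A hold is an interruption if a dose is withheld "without a confirmed clinician decision to permanently discontinue treatment or initiate a new line of treatment". The only length attached to it is a lower bound: "The time interval between doses will be >2 treatment cycles (+ 7-day grace periods".

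Section 8.7.2.4 plans a Kaplan-Meier summary of DoT. It defines persistence as "the proportion of patients still on treatment at specified time points, including 3-, 6-, 12- and 15-months of follow-up", and adherence as total duration of treatment over total follow-up time. It does not say when a patient is no longer on treatment.

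A dose-based rule does exist. Section 8.3.1 defines active treatment exposure periods that run to the last dose + 70 days or to the end of the post-index treatment period, whichever is first. Section 8.7.2.3 applies them to the key secondary analyses only. Table 3 collects the date of every administration.

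**The concern.** Two rules combine badly. DoT ends at a charted decision or another listed event, and an interruption has no upper limit. The interruption rule also measures an interval between two doses, which does not exist when no further dose is given. Such a patient has no measurable interruption, has not discontinued, and stays inside DoT.

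Dose holds matter in this study. Section 6.1 cites keratopathy in 71% of patients at 2.5 mg/kg in the pivotal trial, against 3% with permanent discontinuation related to ocular reactions. Section 7.2 makes the impact of ocular events on interruption, delay and discontinuation an objective. A DoT that counts unresumed undosed time as treatment can be read as tolerability that was not there. It also carries site differences in how promptly a stop is charted into the result, and it can distort the planned comparison of interrupted with continuous treatment in Section 8.7.2.5.

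**Working it through.** The protocol gives no figure that depends on this definition, so there is none to reproduce. The check applies the definitions to dosing histories.

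**Inputs.** The cycle is "dosing interval, which is 21 days (with a real-world scheduling grace period of +7 days". The active exposure window is 70 days (8.3.1), follow-up is 15 months and the planned sample is about 150 (8.5). One month is taken as 30.44 days, so 15 months is 456.6 days.

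**1. Two doses, then held.** Doses on days 1 and 22, no re-dosing, no stop decision, no new line, death at month 9.
- As written: DoT = 9.0 months. On the inferred reading the patient is persistent at 3 and 6 months. If adherence uses DoT, it is 9.0/9.0 = 100%.
- Last dose + 21 days: day 22 + 21 = day 43, and 43/30.4 = 1.4 months. Persistent at neither time.
- Excess: 9.0 − 1.4 = 7.6 months.

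**2. Sensitivity to the window.** Doses on days 0, 21 and 42 after index, then held, alive and followed to month 15, no decision and no new line.

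| End of treatment | Days | DoT (months) | On treatment at 3 / 6 / 12 / 15 months | DoT ÷ follow-up |
|---|---|---|---|---|
| As written | 456.6 | 15.0 | yes / yes / yes / yes | 100% |
| Last dose | 42 | 1.4 | no / no / no / no | 9% |
| Last dose + 28 (cycle plus grace) | 70 | 2.3 | no / no / no / no | 15% |
| Last dose + 70 | 112 | 3.7 | yes / no / no / no | 25% |

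The choice of window changes the answer at 3 months but not at 6, 12 or 15.

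**3. Decision charted late.** With the last dose at 1.4 months and the decision recorded 1, 2, 3 or 6 months later (assumed range), DoT as written is 2.4, 3.4, 4.4 or 7.4 months.

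**4. Cohort effect.** If a share *h* of patients is in an unresumed hold at month 6, persistence is overstated by *h*. The documents give no value for *h*. For *h* = 0, 5% and 10% of 150, that is 0, about 8 and 15 patients, or 0, 5 and 10 percentage points.

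**5. Plausibility of *h*.** Section 6.1 cites a median PFS of 2.8 months. If PFS is exponential (assumption), the fraction progression-free at month 6 is exp(−0.693 × 6/2.8) = 0.23. Then *h* = 10% equals 0.10/0.23 ≈ 44% of those progression-free, and *h* = 20% about 88%. Progression is a listed discontinuation reason in Table 3, so 10% is already a generous upper end.

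**6. Knock-on of moving the end of DoT itself.** DoT is identical to the post-index treatment period, and that period truncates the active exposure window. Ending it at last dose + 21 days would cut the final window from up to 70 days to 21 in the key secondary ocular analyses. A dose-based end therefore has to be a separate quantity.

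**The case against.** The strongest defence is that this is a choice, not a slip. Section 8.3.1 describes DoT as the duration of the line of treatment and defines drug exposure separately, so intent and exposure are deliberately kept apart. That stands as a reason to keep the decision-date version. It does not justify reporting that version alone as treatment duration, nor using it for adherence, where it cannot show missed doses.

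Second, long uncharted stops may be rare. Data are collected about every 3 weeks (Section 5), automated queries are planned (8.9.2), and Table 3 allows a treatment status change to be derived retrospectively. A new line, study exit or death also ends DoT. This limits the size of the effect, but 8.3.1 still requires a recorded decision.

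Third, holds are not hidden. Their duration and reasons are an objective (7.2). Section 8.7.2.4 reports numbers, timing, duration and later treatment patterns for those due to ocular events. This stands too, although the duration of a hold with no next dose has no stated rule.

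A reader might go further in two ways that the documents do not support. One is that the protocol explicitly ends persistence at the recorded decision. It does not: being on treatment is undefined in 8.7.2.4, the statistical analysis plan is not at hand, and the reading is an inference from the only definition of stopping. The other is that more holds would make persistence look better. Compared with continued dosing, a hold leaves persistence unchanged; it looks better only compared with a charted stop.

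**Conclusion.** The concern holds for DoT on the text of Section 8.3.1, and by inference for persistence and adherence. It is a stated rule that gives a misleading result for one kind of patient, not detail left for later.

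For an individual the excess can be large: 7.6 months in the first example, and 11.3 months in the second even against last dose + 70 days (15.0 − 3.7). For the cohort it is unknown. The 0–10 points on 6-month persistence rests on an assumed share of unresumed holds. A reader might infer a larger bias, but the documents give no hold rate, and the cited 2.8-month median PFS argues against one.

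These are descriptive, other secondary outcomes with no hypothesis tested, and the primary objective is untouched. The change is still worth making because it is cheap and the dose dates are collected.

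**What to change.** Leave the post-index treatment period, the data-collection windows and the 70-day active exposure periods unchanged. In Sections 8.3.1 and 8.7.2.4, add a separate dose-based end of treatment for DoT, persistence and adherence, with one pre-stated gap used throughout, for example the protocol's own 70 days:

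- If no later dose is given within follow-up and the gap has elapsed, treatment ends at the last dose plus a stated interval, or at an existing end event if earlier. Setting the interval equal to the gap avoids two competing cut-offs.
- If the gap has not elapsed at the end of follow-up or at study exit (not death) and no stop decision is recorded, the patient is censored as on treatment.
- A hold followed by re-dosing stays inside DoT.

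State that persistence uses this end, and which duration is the numerator of adherence. Report the results beside the decision-date version, labelled as line-of-treatment duration.

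The cost is some wording and a little more analysis, with no new data. Reported DoT and persistence will be shorter, and some genuine holds late in follow-up will be classed as ended. This is an analysis definition only and sets no clinical rule for stopping or re-dosing.

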As shown in [Figure 1](#), eligible RRMM patients from sites who received their first belantamab mafodotin dose before study enrolment will only be invited for study participation if this is deemed necessary based on the enrolment rate in the EU.

Belantamab mafodotin use and ophthalmic monitoring data will be collected while patients are on treatment. Safety and effectiveness data will be collected regardless of whether patients are on treatment or have discontinued treatment during follow-up.

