8.3.2. Baseline Characteristics

For the primary objective of characterizing RRMM patients treated with belantamab mafodotin per routine clinical care, data at the time of the first belantamab mafodotin dose (i.e., the index date) or from the initial MM diagnosis until the index date (i.e., the

baseline period) will be collected retrospectively or at study enrolment, where applicable. Data to be collected are shown in [Table 2](#).

Table 2 Demographics, disease and treatment history

Item	Variable	Definition	Timing
Demographics	Date of birth	Year of birth	Index date
	Sex	Categorical variable: 
 • Male • Female 	Index date
	Height	Continuous variable	Index date
	Weight	Continuous variable	Index date
	ECOG Performance Status	Categorical variable: 
 • 0 • 1 • 2 • 3 • 4 	Index date
MM History	Date initial diagnosis	Date of first MM diagnosis	Baseline period
	Extramedullary disease	Categorical variable	Baseline period
	ISS stage	Categorical variable: stage at initial MM diagnosis 
 • I • II • III 	Baseline period
	MM subtype	Categorical variable: subtype at initial diagnosis 
 • IgG • IgA • IgM • IgD • Biclonal (G,A) • Light chain MM • Other 	Baseline period
	Cytogenetic risk	Categorical variable: 
 • High [e.g., t(4;14), t(14;16), del17p] • Standard 	Baseline period
	Progression status	Categorical variable: disease progression (per IMWG criteria or to local standard practice) on last line of therapy: 
 • Yes • No 	Baseline period
	Refractory status	Categorical variable: 
 • Triple refractory • Quad refractory • Penta refractory 	Index date

Item	Variable	Definition	Timing
MM Treatment History	Prior MM therapies	Categorical variable: therapy type* by line per EHA-ESMO (Dimopoulos, 2021) and NCCN guidelines (Kumar, 2020)	Baseline period
	Dates of prior MM therapies	Date of first and last dose of each prior therapy	Baseline period
Medical History	Pre-existing comorbidities	Categorical variable: type of comorbidity** per category such as: 
 • Renal diseases • Pulmonary diseases • Cardiac diseases • Diabetes • Eye diseases including history of dry eye/eye injuries affecting the BCVA • Other 	Baseline period

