8.3.3. Belantamab Mafodotin Treatment

Belantamab mafodotin treatment data to be collected during follow-up from standard of care visits are shown in [Table 3](#). Data will be collected from the time of the first belantamab mafodotin dose until permanent discontinuation of belantamab mafodotin treatment, the end of follow-up at 15 months, study discontinuation for any reason, informed consent withdrawal or death; whichever comes first.

Table 3 Belantamab mafodotin treatment

Variable	Definition	Timing
Date(s) of Administration	Date of each administration	Index date and post-index treatment period
Dose	Continuous variable: prescribed and administered doses	Index date and post-index treatment period
Treatment status change	Categorical variable: prospectively captured or derived retrospectively 
 • Dose modification • Treatment interruption / delay • Discontinued 	Post-index treatment period
Primary reason dose modification	Categorical variable: 
 • Any AE • Other 	Post-index treatment period
Primary reason treatment interruption/delay	Categorical variable: 
 • Any AE • Patient decision unrelated to AEs • Other 	Post-index treatment period
Primary reason treatment discontinuation	Categorical variable: 
 • Disease progression • Any AE • Patient decision unrelated to AEs • End of treatment • Death (unrelated to therapy) • Other 	Post-index treatment period
Concomitant Medications	Categorical variable: type of concomitant medication* Continuous variable: dose at index date for each concomitant medication	Index date and post-index treatment period

Abbreviations: AE=adverse event.

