8.6. Data Management

All information outlined in Section 8.3 will be recorded prospectively directly into an eCRF or retrospectively from medical records, if applicable, into the study database.

Data collection will be completed in a suitable electronic data capture (EDC) platform (Veeva EDC). All data collected will be stored at secure servers ensuring compliance with local or national regulations. Database lock is anticipated on the date the study is closed, i.e., when all documents and data have been collected, and reviewed and necessary data changes have been made after the last visit for the last subject. Additional details regarding data collection and validation procedures will be detailed in a data management plan.

The investigator is responsible for ensuring data is entered in a timely manner and verifying that data are accurate and correct. When the study is completed, the investigators must retain essential documents, e.g., source data that support information entered in the eCRF, for as long as needed to comply with regulatory guidelines and Sponsor requirements. The investigator must permit study-related monitoring, audits, institutional review board (IRB) review, and regulatory agency inspections and provide direct access to source data documents. The investigator will notify the Sponsor prior to moving or destroying any of the study documents. No records may be destroyed during the retention period without the written approval of the sponsor. No records may be transferred to another location or party without written notification to the sponsor.

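### DoT and the interruption rule depend on the start date of a new line of treatment, which no collection table in the protocol lists

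*Protocol*

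**What the plan says.** Protocol Section 8.3.1 defines the post-index treatment period as the DoT. It runs from the first dose to the earliest of a confirmed decision to stop permanently, the "confirmed date of a new line of treatment or the date of the end of follow-up at 15 months", study discontinuation, withdrawal of consent or death. Discontinuation is "a recorded clinician decision (with an associated decision date) to permanently discontinue belantamab mafodotin treatment". An interruption is one or more withheld doses "without a confirmed clinician decision to permanently discontinue treatment or initiate a new line of treatment".

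Section 8.3.3 collects treatment data from the first dose "until permanent discontinuation of belantamab mafodotin treatment, the end of follow-up at 15 months, study discontinuation for any reason, informed consent withdrawal or death". Section 8.3.4 gives the same list for ophthalmic monitoring. Neither list includes a new line of treatment.

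On therapies other than belantamab mafodotin, Table 2 asks for "Date of first and last dose of each prior therapy", in the baseline period only. Section 8.6 ties the database to this part of the protocol: "All information outlined in Section 8.3 will be recorded prospectively directly into an eCRF", or retrospectively from medical records. Section 8.1 adds: "Safety and effectiveness data will be collected regardless of whether patients are on treatment or have discontinued treatment during follow-up".

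**The concern.** An endpoint is defined by a date that the data collection plan does not list. A statistical analysis plan can set rules for using a date, but it cannot supply one that was never captured.

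Discontinuation needs a recorded decision with its own date. If doses stop, another regimen begins and the site enters no such decision, nothing in the listed data closes the treatment period at the switch. The outputs in Section 8.7.2.4 that rest on that closing date are DoT, time to discontinuation, persistence at 3, 6, 12 and 15 months, adherence (taking its numerator as DoT) and the duration of interruptions. The error always runs upward.

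A second effect concerns response. ORR in 8.3.1 takes the best response over the study period, 8.7.2.4 takes it over follow-up, and effectiveness data continue after treatment stops. A response achieved on a later regimen could therefore be counted, and no new-line date is available to identify it.

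**Working it through.** The plan states no figure to reproduce. The check is of the definitions against the data list, followed by an illustration of size.

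**1. Is the next line collected anywhere?**

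| Protocol table | Content | Gives a new-line start date? |
|---|---|---|
| 2 | Prior myeloma therapies and their dates, baseline period | No |
| 3, status and reasons | Dose modification, interruption/delay, discontinued; reasons for each | No: a new line is neither a status nor a listed reason |
| 3, concomitant medication | Type; dose at index date | No: no start date and no line flag. Its timing is bounded by the treatment period, whose end needs the missing date |
| 4 and 5 | Ophthalmic monitoring; ocular AESIs | No |
| 6 | Date of death; tumour response | No |
| 7 | Treatment history at baseline only; no subsequent-therapy row at visits | No |

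**2. Do the windows agree?** 8.3.1 closes the treatment period at a new line. The collection text in 8.3.3 and 8.3.4 does not, although Tables 3 and 4 in those sections use the treatment period as their timing. The passages need reconciling.

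**3. One patient.** Assumed, in days from the index date: last dose on day 64, new regimen on day 110, no stop decision entered, alive and followed to month 15.

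- Follow-up: 15 × 30.4375 = 456.6 days.
- DoT under the protocol's rule: 110 days. From the listed data: about 456 days, an excess of about 346.
- Adherence (treatment days ÷ follow-up days): 110 ÷ 456.6 = 0.24 under the rule, 1.00 from the listed data.
- Active exposure is the earlier of last dose + 70 days and the end of the treatment period. With the new-line date it ends on day 110. Without it, it ends on day 64 + 70 = 134. The difference is 24 days.

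**4. A group, conditional on an assumed share.** Let S(t) be the true proportion still on treatment, taken as exponential, and u the share of stoppers who switch with no recorded decision. With deaths ignored, reported persistence is S(t) + u × (1 − S(t)). The apparent KM median DoT is the time at which S = (0.5 − u) ÷ (1 − u). A median of 2.8 months borrows the pivotal study's PFS median from Section 6.1 as a stand-in for DoT. A median of 5 months is an assumption for comparison.

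| True median | True 12-month persistence | Reported: u = 5% / 10% / 20% | Apparent median DoT, months |
|---|---|---|---|
| 2.8 months | 5.1% | 9.9% / 14.6% / 24.1% | 3.0 / 3.3 / 4.0 |
| 5 months | 18.9% | 23.0% / 27.1% / 35.2% | 5.4 / 5.9 / 7.1 |

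For example, with a median of 2.8 and u = 10%: 0.051 + 0.10 × 0.949 = 0.146. Because the excess is u × (1 − S), the table largely restates the assumed u, which the documents do not give. Deaths would reduce it: an exponential OS with the quoted 13.7-month median leaves 0.5^(12/13.7) = 55% alive at 12 months.

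**The case against.** The strongest reply is that the date is covered. Section 8.6 promises to record all information in 8.3, and the new-line date is named within 8.3.1. Figure 3 and the eCRF are not shown, so no one can say from these documents that the eCRF lacks the field. That limit stands. It remains true that the protocol makes the date a variable in no table.

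Next, a new myeloma drug could surface as a concomitant medication at three-weekly chart review, and because 8.3.3 omits the new-line stop, collection would still be open when no decision is entered. This is fair, but a drug type without a start date or line does not give a confirmed new-line date. Table 3 also allows status changes to be derived retrospectively and lists disease progression as a discontinuation reason, so many switches may carry a stop decision. Dose gaps could support sensitivity analyses, since every administration date is collected. These points reduce the problem but do not let the protocol's own rule be applied.

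Three stronger readings are tempting, and the documents do not support them.

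- A reader might infer that every switcher is classed as interrupted, with DoT running to month 15. The definition excludes patients with a confirmed decision to start a new line. Misclassification arises only when neither the stop decision nor the new line is recorded, and month 15 is only the latest possible end.
- A reader might infer that about half the cohort is affected. Exponential curves through the quoted medians (PFS 2.8, OS 13.7 months) put 0.738 − 0.226 = 51% (about 77 of 150) alive after progression at 6 months, and 0.468 − 0.024 = 44% (about 67) at 15 months. That counts patients who might receive a next line, not unrecorded switchers. The PFS curve also fits poorly with the quoted 32% ORR and 11.0-month median DoR. Assuming responses start at 1 month and DoR is exponential, 0.32 × 0.5^(14/11) = 13% would be progression-free at month 15 from responders alone. That leaves about 34% (50 patients) alive after progression.
- A reader might infer that nothing after a switch can be separated from belantamab mafodotin. Section 8.7.2.3 describes the key secondary objectives during active treatment exposure periods, which are capped at last dose + 70 days, and the OS and rwPFS definitions do not use a new-line date.

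**Conclusion.** The mismatch is real and lies within Section 8.3. Two definitions rely on an event that Tables 2 to 7 do not collect, and two collection windows leave it out. The harm is conditional: it needs a patient who starts another regimen with no recorded stop decision. For such a patient the excess can be large, about 346 days in the example, and always in the direction of longer treatment. The number of such patients is unknown, so no cohort-level bias can be stated as fact, and the group table holds only for its assumed shares.

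The effect falls on other secondary measures, and on best response where it is reached on a later regimen. The primary objective is a baseline description and is untouched, in a study that tests no hypotheses. The point should be corrected because the missing item cannot be reliably restored at the analysis stage.

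**What to change.** - Add to Table 6 (timing: post-index period), and as a row at standard of care visits in Table 7, the first subsequent anti-myeloma therapy: start date and regimen.
- Align the collection windows in 8.3.3 and 8.3.4 with the treatment period in 8.3.1.
- State that, for analysis, the start of a new line ends DoT and counts as a discontinuation event on that date when no earlier decision date is recorded.

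These are data and analysis definitions and leave patient management unchanged. The cost is a small amount of added site data entry, from charts that Section 5 already has reviewed every three weeks, plus the eCRF and protocol wording.
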